4.2 Secondary Outcomes

4.2.1 Interference due to Pain

BPI #9 will be assessed at intervals defined in the Schedule of Study Procedures. This question asks subjects to rate how pain has interfered with various aspects of life: "Mark the box beside the number that describes how, during the past 24 hours, pain has interfered with your: (a) General activity (b) Mood (c) Walking ability (d) Sleep (e) Enjoyment of life." Responses are recorded on an 11-point scale from "0" to "10" with "0" defined as "Does Not Interfere" and "10" defined as "Completely Interferes."

4.2.2 Patient Global Impression of Change (PGIC) Scale

Participant ratings of global improvement are one of the core outcome domains in chronic pain studies (Dworkin et al. 2005). Patient Global Impression of Change (PGIC) Scale is assessed at intervals defined in the Schedule of Study Procedures, which rates perception of change in activity limitations, symptoms, emotions, and overall quality of life in relation to pain since beginning treatment. The scale ranges from 0 defined as "No change" to 7 defined as "A great deal better, and a considerable improvement that has made all the difference." Responses are collected by telephone or outpatient office evaluations in the Interventional Pain Clinic.

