5.5.4 Visits 3, 4 and 5: Weekly telephone follow-up evaluations

Visits 3, 4 and 5 consist of weekly telephone evaluations at 1, 2 and 3 weeks after starting peripheral nerve stimulation (Group 1) or discontinuation of peripheral nerve block (Group 2). If issues related to the peripheral nerve stimulator device or leads occur and cannot be resolved by telephone, subjects may be evaluated in the Interventional Pain Clinic as needed.

Subjects are asked to rate their worst, least, and average PLP and RLP (BPI #3, #4, and #5). A medical reconciliation will be completed during each phone evaluation by asking the subject how many pills of narcotic pain medications they have left and querying the Virginia Prescription Monitoring Program Database.

5.5.5 Visit 6: First outpatient clinic evaluation / 30 days after start of PNS

All subjects are asked to return to the Interventional Pain Clinic at 4 weeks after the start of peripheral nerve stimulation. Stimulator devices (Group 1) will be inspected to ensure appropriate function. Lead exit sites are inspected for skin irritation, infection, and inflammation. Maintenance, care of the leads and lead exit sites, and bandage changes will be performed as needed.

All subjects are asked to rate their worst, least, and average PLP and RLP (BPI #3, #4, and #5). Subjects will rate the degree with which pain has interfered with general activity, mood, walking ability, sleep, and enjoyment of life (BPI #9). Pain Disability Index (PDI) and Patient Global Impression of Change (PGIC) will be assessed. A medical reconciliation will be completed during each phone evaluation by asking the subject how many pills of narcotic pain medications they have left and querying the Virginia Prescription Monitoring Program Database.

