6.3 Data Analysis

A table of outcome measures recorded during the study can be found in Appendix. Scores rating daily 491 492 average, worst, and least pain will be compared between groups. Changes in pain will be evaluated for

individual subjects and compared between groups. For each subject, mean pain scores over the first and 493

494 second months following TFA or TTA surgery will be calculated. An overall mean across all subjects will

be calculated. Additionally, sub-analyses will be performed to determine if there is a difference in these 495

outcomes between groups over different post-operative phases (such as acute (e.g. days 1-30) or subacute 496

497 (e.g., 1-3 months), or chronic (e.g. >3 months)). Statistical analysis will be performed with two-sample t-

498 test, and p-values will be reported without adjustment, consistent with feasibility study design and the

499 number of subjects.

500 Pain medication usage will be recorded in subject diaries and obtained during follow up encounters. Opioid

medication use will be analyzed by averaging 24-hour morphine equivalent dosing (MED) over each 501

502 follow-up interval and comparing groups. Changes in opioid medication use will be reported for individual

503 subjects by calculating morphine equivalent dosing (MED). Average MED will be calculated and compared between groups. The time to cessation of opioid use will be reported. Side effects associated 504

with opioid use will be assessed at each visit and the number of side effects occurring over various intervals 505

506 will be recorded. Analgesic-related outcomes will be compared between the Groups.

507 Patient Global Impression of Change (PGIC), Pain Catastrophizing Scale (PCS), and Pain Disability Index

508 (PDI) scores will be averaged for each group and compared. Data regarding functional outcomes

509 (Functional Independence Measure [FIM] score), time to wound healing, incidence of neuromas, prosthesis

fitting, time to hospital discharge, 30-day readmission rate, and hospital discharge survey will be compared 510

between groups. 511

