7.2.7 Discomfort or increased pain on insertion, during use or with withdrawal

Like procedures involving percutaneously inserted needles (e.g., injections, needle electromyography, acupuncture), discomfort associated with test stimulation/placement of the stimulator lead is possible. Usually the discomfort is transient and improves shortly after needle insertion. Subjects are asked to provide feedback on pain or discomfort experienced during the procedure. Symptomatic relief with local anesthesia may be used to reduce discomfort.

Electrical stimulation is perceived by the subject as tingling or vibratory sensations. These sensations are expected to be comfortable, however it is possible that they can cause discomfort or pain. Uncomfortable sensations are likely directly related to stimulus intensity, which is adjusted on the PNS stimulator. Pain is typically associated with higher intensity levels. During the lead placement procedure, stimulus intensity is adjusted to the determine the minimum and maximum range of intensities that produce comfortable

sensations without discomfort or pain. Prior to completion of the lead placement procedure, an appropriate stimulation intensity is set. Further, the subject can select from a range of intensities determined by the investigators as safe and unlikely to cause discomfort. If a subject ever feels pain related to stimulation, they can turn down the intensity or turn the stimulator off.

Subjects may experience worsening of pain symptoms or may not obtain any therapeutic benefit from the system. Worsening pain could be caused by natural changes in pain during post-operative recovery and rehabilitation, or may be caused by electrical stimulation, or the presence of the lead. This is a common risk, but worsening pain is expected to be transient, resolving without additional treatment. Subjects can have their stimulation parameters adjusted throughout the study for optimal comfort, or treatment may be discontinued. These risks are mitigated by clinical training on the safe limits of stimulation and the proper placement of the leads.

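### The PGIC in 4.2.2 has no score for worsening, and its reference point, the start of treatment, is undefined, most clearly for the control group

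*Combined protocol and SAP*

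**What the plan says.** Section 4.2.2 presents the PGIC as a rating of perceived change. It gives only the two ends of the scale. For the lower end it states: "The scale ranges from 0 defined as 'No change' to 7 defined as". The label attached to the top score is "A great deal better, and a considerable improvement that has made all the difference". The subject rates "overall quality of life in relation to pain since beginning treatment", and the start of treatment is not defined for either group.

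The measure is taken in both groups. For Visit 6, which all subjects attend, section 5.5.5 states: "Pain Disability Index (PDI) and Patient Global Impression of Change (PGIC) will be assessed". The Appendix schedule also marks PGIC at the 3, 6 and 12 month calls. Its 8-week column cannot be read reliably in the extracted text.

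Section 6.3 lists PGIC with the catastrophizing and disability scales and says that the "scores will be averaged for each group and compared".

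On the possibility of deterioration, section 7.2.7 says: "Subjects may experience worsening of pain symptoms or may not obtain any therapeutic benefit from the" system. It classes worsening pain as a common risk, which section 7.2 defines as more than 10%, and adds that it is expected to be transient.

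**The concern.** There are two separate weaknesses.

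**Floor.** The scale is described as measuring change, but its lowest point is no change. A worsened subject is recorded together with an unchanged one. Because the planned summary is a group mean, every such subject makes that arm look better than it is. If worsening is more frequent in one arm, the comparison understates the difference, whichever arm is worse off.

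**Reference point.** Group 1 starts a distinct new treatment by post-operative day 7. Group 2 has only standard medical therapy, which section 3.2 describes as the routine care every patient gets, enrolled or not. A control subject asked about change since treatment began has no study event to think back to. Different subjects, and the two arms, may therefore answer different questions.

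Section 6.1 says that the pilot will be used to refine assessment procedures for a larger trial, so an unclear instrument could be carried forward.

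**Working it through.** The plan gives no expected PGIC value, SD or power figure, so there is no planned number to reproduce. The sample size (16, 8 per arm) is justified as a pilot and is not affected by this point.

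**1. One subject at a time (8 per arm, section 6.1).** Suppose one subject would have answered −k on a two-directional scale and is recorded as 0. The arm mean rises by k/8.
- k = 1: 1/8 = 0.125
- k = 3: 3/8 = 0.375
- k = 7 (a scale mirrored to −7, assumed): 7/8 = 0.875

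**2. Group means under an assumed distribution.** Let the true change X be normal with mean μ and SD σ in PGIC points. Values of μ and σ are assumed. The upper limit of 7 and whole-number scoring are ignored. The recorded mean is

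E[max(X, 0)] = μ·Φ(μ/σ) + σ·φ(μ/σ).

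Example with σ = 2. For μ = 2: 2 × 0.8413 + 2 × 0.2420 = 2.17. For μ = 0: 2 × 0.3989 = 0.80. The recorded difference is 1.37, against a true difference of 2.

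| True means, Group 1 v Group 2 | SD | Recorded means | Recorded difference |
|---|---|---|---|
| 3 v 1 | 2 | 3.06 v 1.40 | 1.66 |
| 3 v 1 | 3 | 3.25 v 1.76 | 1.49 |
| 2 v 0 | 2 | 2.17 v 0.80 | 1.37 |
| 2 v 0 | 3 | 2.45 v 1.20 | 1.26 |
| 1 v −1 | 2 | 1.40 v 0.40 | 1.00 |
| 1 v −1 | 3 | 1.76 v 0.76 | 1.00 |
| 0 v −2 | 2 | 0.80 v 0.17 | 0.63 |
| 0 v −2 | 3 | 1.20 v 0.45 | 0.74 |
| −1 v 1 | 2 | 0.40 v 1.40 | −1.00 |
| −1 v 1 | 3 | 0.76 v 1.76 | −1.00 |

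Three things follow.
- A true difference of 2 is recorded as 0.63 to 1.66 in these cases. The loss is greatest when the means are low.
- If Group 1 is the worse arm (−1 v 1), half the difference is lost.
- An arm with no average change records 0.80 to 1.20, which reads as improvement.

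The shrinkage assumes the same SD in both arms. With equal true means of 0 but SDs of 2 and 3, the recorded means would be 0.80 and 1.20, a difference of 1.20 − 0.80 = 0.40 where none exists.

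**3. Reference point.** The documents allow several readings of the start of treatment.
- Both arms count from standard therapy, which both receive (section 3.2): gap zero.
- Each arm uses its weekly visit clock (sections 5.5.4 and 5.5.6), which is the start of stimulation in Group 1 and the end of the nerve block in Group 2. Visit 1 comes at least 24–48 hours after catheter removal and lead placement follows it (section 5.5.1), so the gap is at least about 1 to 2 days.
- Group 2 counts from block placement, the day before or the day of surgery (section 5.5), and Group 1 from stimulation by day 7: up to 7 − 0 = 7 or 7 − (−1) = 8 days, an interval that includes surgery or the first days after it, and block removal.

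The other visit clocks do not settle it. Section 5.5.5 times Visit 6 for all subjects from the start of stimulation, an event that Group 2 does not have. Section 5.5.8 times the late calls from enrollment in both arms.

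**The case against.** The strongest reply is that little is lost. BPI items #3, #4 and #5, the primary pain measures, run from 0 to 10 and can move either way. So can BPI #9 and the PDI, both with a baseline. Section 8.1 has subjects asked about increased discomfort or pain at each follow-up encounter. A reader might infer from the PGIC wording that harm would go unseen in this trial. The documents do not support that: worsening is lost only on the PGIC. This part of the reply stands.

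Section 7.2.7 also expects worsening to be transient, while the PGIC is marked from 4 weeks onward, so few subjects may be worse than at the start when asked. That is fair and bears on the size. It does not supply the missing response.

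A reader might also infer that the two arms do rate change from different starting points. The documents do not say so. They leave the term undefined, and a common anchor at the start of standard therapy is a possible reading. Even the widest gap of about 7 to 8 days is short beside recall over 4 weeks to 12 months. What stands is narrower: the anchor is undefined and may differ.

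Finally, the PGIC form is not in the documents, and its full list of responses may be wider than 4.2.2 suggests. If so, 4.2.2 needs correcting to match it.

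**Conclusion.** The concern holds in a limited form. As 4.2.2 is written, worsened and unchanged subjects share the lowest PGIC score, and the averaging in 6.3 turns this into an inflated mean in any arm where subjects worsen. With similar spread in the two arms, the between-group difference shrinks. The inflation of the arm mean follows from the scale itself. The amount does not: the figures of 0.63 to 1.66 for a true 2 points rest on assumed means, assumed SDs and normality, and are illustrative only.

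The reference point is undefined, most clearly for Group 2, and may differ between arms. No size or direction of bias from this can be derived from the documents.

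The consequence is modest: one secondary outcome in an unblinded pilot of 8 per arm, with other measures able to record worsening. It is worth correcting because the correction is cheap and the pilot is meant to test its assessment procedures.

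**What to change.** In 4.2.2 and on the PGIC form, list every response option and let them run in both directions, from worse through no change to better. Replace the undefined reference to the start of treatment with one event that both groups have. The Visit 1 baseline would serve. Use the same wording for clinic and telephone administration in both groups.

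The change needs no added visits or subjects. On what the documents show, it is a matter of protocol and form wording. The downside is that scores would not be directly comparable with the one-directional version, including any already collected on it.

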4.2.3 Pain Disability Index (PDI)

The Pain Disability Index (PDI) a simple and rapid instrument for measuring the impact that pain has on the ability of a person to participate in essential life activities. This can be used to evaluate patients initially to monitor them over time and to judge the effectiveness of interventions. The index was developed at St. Louis University Medical Center. PDI) is assessed at intervals defined in the Schedule of Study Procedures, which measures subjects' disruption in various aspects of life secondary to **chronic pain**, including family/home responsibilities, recreation, social activity, occupation, sexual behavior, self-care, and life-support activities. Each category is rated on an 11-point scale from "0" to "10" with "0" defined as "No Disability" and "10" defined as "Worst Disability." Responses are collected by telephone or outpatient office evaluations in the Interventional Pain Clinic.

4.2.4 Pain Catastrophizing Scale (PCS)

The PCS is a widely-used, validated and reliable 13-question instrument to assess rumination (4 questions), magnification (3 questions), and helplessness (6 questions) (Sullivan, 2009.; Osman et al. 1997). The survey asks participants to think back on painful experiences in the past and reflect on how often they had specific thoughts or feelings. Each question is scored on a 0-4 scale with 0 = "not at all" and 4 = "all the time". Higher scores indicate a greater tendency towards catastrophizing pain, which has been correlated with worse postoperative pain and response to pain therapies (Riddle et al 2010; Pavlin et al 2005; Forsythe et al 2008).

4.2.5 Analgesic use and Opioid-related Side Effects

All opioid and nonopioid pain medication use will be assessed at intervals according to the Schedule of Study Procedures. The Virginia Prescription Monitoring Program Database will be queried. Subjects will be asked if they are taking any medications for pain. Subjects will be asked to count their remaining number of pills of narcotic pain medication at each follow-up encounter.

4.2.6 Functional Independence Measure (FIM)

The FIM provides a uniform system of measurement for disability based on the International Classification of Impairment, Disabilities and Handicaps. The FIM instrument measures the level of a patient's disability and indicates how much assistance is required for the individual to carry out activities of daily living. A baseline mobility FIM will be recorded with the assistance of the Department of Physical Therapy shortly after amputation but before stimulator placement (Group A) and follow-up FIM will be recorded at the 4 and 8-week outpatient clinic visits. Improvement in FIM will be evaluated and compared between groups.

4.2.7 Patient Outcomes and Hospital Discharge Survey

Other secondary outcomes including time to prosthesis fitting, wound healing, incidence of neuromas, time to hospital discharge 30-day readmission rate, and hospital discharge survey will be documented from the electronic medical record and compared between groups.

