- The duration of this investigation is expected to be 18-24 months. We anticipate enrolling 2-4 patients per 454
- month. Each patient's participation will last approximately 12 months. 455

Data Management 6.0

Sample Size

- The investigation seeks to broaden the knowledge of the effects of neuromodulation on acute post-operative 458
- pain in nontraumatic lower extremity amputation. The aim is to evaluate the feasibility of implementing 459
- PNS in TFA or TTA in the acute post-operative period. 16 subjects will be randomized into two groups 460
- 461 with 8 each. Sampling will not be restricted by race or gender. The sample size of 16 is expected to allow
- the investigators to conduct a cost-effective yet informative pilot study to assess the logistics of placing the 462
- 463 device as described in this protocol, evaluate safety, and report any clinically significant differences in
- primary and secondary outcomes between Treatment and Control Groups. The study outcomes will be 464
- 465 reported in nontraumatic TFA or TTA, many of which are secondary to dysvascular disease. Although this is a specific subset of all amputations that are performed, dysvascular disease accounts for a sizeable 466
- proportion of limb loss in the US with an estimated prevalence of 38-82% (24, 25). The results of this 467
- investigation will be used to refine the study design, recruitment, randomization, retention, and assessment 468
- 469
 - procedures, and ultimately develop a larger, multicenter, randomized controlled trial to further evaluate

470 treatment efficacy, adverse effects, and cost efficiency. To improve generalizability, subsequent

471 investigations will seek to include a wider subset of amputations which may be accomplished with the

472 addition of more study sites.

473

490

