6.2 Sampling and Randomization Procedures

Based upon historical data on amputations at the HHM-VAMC, there are estimated to be one to two 474 475 amputations per week that would qualify for enrollment in this study. Subjects will be screened for enrollment through the vascular surgery clinic. A considerable proportion of vascular clinic patients will 476

require lower extremity amputation and are usually scheduled for next day surgery due to the urgency of 477

presentation. Study investigators will conduct a chart review of potential subjects and complete Form 01-478

479 A (screening and demographic information). Based on the chart review, if a patient appears to meet all 480

eligibility criteria, then they will be contacted by study investigators for potential enrollment. If the patient

agrees to participate, they will be consented and randomized to Group 1 or Group 2. 481

482 Prior to the start of this study, a member of the study staff that is not involved with recruitment or data

483 evaluation will be responsible for generating a random string of group assignments long enough to fill all

anticipated spots in this study. The numbers will be placed in secure envelopes by blocks of two. A block 484

485 of two will contain one assignment to the Treatment Group and one assignment to the Control Group. As

486 subjects are consented and enrolled in the study, they will be assigned an envelope which randomizes them

487 to a group. Subjects are not blinded to their group assignments. Subjects in the Treatment Group will

receive the investigational treatment (30 to 60-days of peripheral nerve stimulation) in addition to SMT. 488

489 Subjects in the Control Group will be treated with the SMT alone.

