10.0 Appendix

Schedule of Study Procedures

									Meds/SE Pain/Sense								Sti	udy F	roce														
Incidence of neuromas	30-day readmission rate	Hospital discharge survey	Time to hospital discharge	Time to prosthesis fitting	FIM	PDI	PCS	PGIC	BPI-9 (interference)	Pain medications	Opioid-related side effects	Phantom sensation	BPI-5 (average pain)	BPI-4 (least pain)	BPI-3 (worst pain)	BPI-2 (pain distribution)	Assess AEs	Remove Lead	Inspect bandages and Lead exit site	Start Stimulation	Lead Placement	Randomize	Beck Depression Inventory	Remove PNB catheter	Informed Consent	Chart Review/Screening		Visit					
																							×	×	×	×	Screen and Consent						
					×	×	×		×	×	×	×	×	×	×	×						×					Baselin	1					
																					×	×	×						Lead placement (Group 1 only)	2			
										×	×	×	×	×	×		×										1 week PNS	3					
	Data collected from medical record	Data collected from medical record								×	×	×	×	×	×		×										2 weeks PNS	4					
Data co			Data co	Data co	Data co	Data co						×	×	×	×	×	×		×										3 weeks	5			
Data collected from medical record			Data collected from medical record	llected fro	×	×	×	×	×	×	×	×	×	×	×		×		×								4 weeks PNS/1st IPC evaluation	6					
m medi			m medi	Data collected from medical record						×	×	×	×	×	×		×										5 weeks	7					
cal recor	cal recor	cal recor	al record							×	×	×	×	×	×		×										6 weeks	8					
٩	d	ď.	_ a		۵	٩		_						×	×	×	×	×	×		×										7 weeks PNS	9	
										×	×	×	×	×	×	×	×	×	×	×		×	×	×								8 weeks PNS/2nd IPC evaluation	10
						×	×	×	×	×	×	×	×	×	×		×										3 month phone	11					
						×	×	×	×	×	×	×	×	×	×		×										6 month phone	12					
						×	×	×	×	×	×	×	×	×	×		×										12 month phone	13					

Literature Cited

- 1. Richardson et al. A prospective study of factors associated with the presence of Phantom limb pain 6 months after major lower limb amputation in patients with peripheral vascular disease The Journal of Pain Volume 8, Issue 10, October 2007, Pages 793–801.
- 2. Hanley M, et al. Pre-amputation pain and acute pain predict chronic pain after lower extremity amputation The Journal of Pain Vol 8, Issue 2, Feb 2007, pg 102-109.
- 3. Liu SS et al. Prolonged Postoperative Pain in Total Knee and Total Hip Arthoplasty Reg Anesth Pain Med 2012; 37-42.
- 4. Hickey OT et al. Preoperative anxiety and catastrophizing: a systematic review and meta-analysis of the association with chronic postsurgical pain Clin J Pain 2010; 26: 556-560.

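### Neuroma incidence is read from the routine record, where detection probably depends on the pain that PNS aims to change; wound healing and readmission from the same source are loosely measured

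*Combined protocol and SAP*

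**What the plan says.** Section 1.2 asks whether PNS affects wound healing, neuromas and readmission, among other outcomes. Section 4.2.7 gives the source: "wound healing, incidence of neuromas, time to hospital discharge 30-day readmission rate, and hospital discharge survey will be documented from the electronic medical record". In the Schedule of Study Procedures (Section 10.0) the neuroma and readmission rows carry the entry "Data collected from medical record". No row for wound healing is legible, although that table is badly extracted.

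Section 6.3 plans to compare "time to wound healing, incidence of neuromas, prosthesis" fitting and the other record-based outcomes between groups. Healing is a time there, whereas Section 4.2.7 names only wound healing.

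The trial is open label: "Subjects are not blinded to their group assignments". No blinded assessor is described. Both arms have scheduled clinic contact: "All subjects are asked to return to the Interventional Pain Clinic at 4 weeks" (Section 5.5.5, Visit 6), and again at about 60 days (Section 5.5.7, Visit 10). Neither visit description lists an examination of the amputation wound or stump.

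**The concern.** Randomisation makes the arms comparable at the start. It does not make them equally likely to have an event found. With no scheduled examination, a neuroma enters the record only when someone looks for it, and residual-limb pain is the obvious reason to look. Sections 1.3 and 7.1 state that PNS is hoped to lower that pain. The chance of detection may therefore lie downstream of treatment, and a lower recorded count with PNS could mean fewer neuromas or only fewer searches.

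The other two outcomes raise a lesser problem. A recorded healing date reflects when a clinician looked and wrote it down. The local record may also miss admissions to other hospitals; Section 5.5 allows for non-veteran participants, whose care may be elsewhere.

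At stake are the answers to the questions in Section 1.2 and, more practically, the assessment methods that the larger trial inherits.

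**Working it through.** **Plan's own figure.** "16 subjects will be randomized into two groups" of 8 (Sample Size, Section 6), with 1:1 allocation in blocks of two. No event rate, effect size or power is given, so there is nothing to reproduce.

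**Neuroma: can a difference arise with no true effect?** All rates here are assumptions, because the documents give none.

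- True neuroma rate: 30% in both arms.
- Probability of work-up: 0.8 if in pain, 0.2 if not.
- Proportion in pain: 75% of controls; 40% or 55% with PNS.

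Recorded incidence = true rate × [P(pain) × 0.8 + P(no pain) × 0.2].

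- Control: 0.30 × (0.75 × 0.8 + 0.25 × 0.2) = 0.30 × 0.65 = 19.5%.
- PNS, 40% in pain: 0.30 × (0.40 × 0.8 + 0.60 × 0.2) = 0.30 × 0.44 = 13.2%; ratio 0.68.
- PNS, 55% in pain: 0.30 × (0.55 × 0.8 + 0.45 × 0.2) = 0.30 × 0.53 = 15.9%; ratio 0.82.

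In patients, at 8 per arm: 8 × 0.195 = 1.56 expected in controls, against 8 × 0.132 = 1.06 or 8 × 0.159 = 1.27 with PNS. The artefact is 0.50 or 0.29 of a patient.

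**Direction.** Setting detection directly, still at a true 30%:

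| Detection, PNS v control | Recorded, PNS v control | Ratio |
|---|---|---|
| 0.6 v 0.6 | 18% v 18% | 1.0 |
| 0.6 v 0.9 | 18% v 27% | 0.67 |
| 0.4 v 0.9 | 12% v 27% | 0.44 |
| 0.9 v 0.5 | 27% v 15% | 1.8 |

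Equal detection, even if incomplete, gives no artefact. More looking in the PNS arm reverses the sign.

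**Against chance at 8 per arm.** Exact enumeration over all binomial outcomes, two-sided 0.05 (assumed; the plan states neither alpha nor sidedness). The t-test is the only test that Section 6.3 names; Fisher's exact test is shown for comparison. Each cell gives the rejection probability under full equal detection, then under 0.4 v 0.9.

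| True rate | t-test | Fisher |
|---|---|---|
| 30% | 5.3% → 6.9% | 1.2% → 1.6% |
| 50% | 7.7% → 20.5% | 2.1% → 7.9% |

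At a true 30%, the arms differ by two or more patients with probability 41% by chance alone, and 46% with the artefact.

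**In a larger trial.** At 200 per arm (an assumed size), a spurious 18% v 27% would be significant 58% of the time, and 12% v 27% would be 97% of the time.

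**Wound healing.** If healing is noted at the first look after it happens, the mean recording delay is half the interval between looks. Looks every 14 v 28 days would give (28 − 14)/2 = 7 days of artefact; 7 v 28 days would give 10.5; equal intervals give 0. The documents do not show that the intervals differ.

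**Readmission.** If a fraction s of admissions is captured in both arms, the observed difference is s × the true difference. With s = 0.6, 60% of a true difference remains, and a true difference of zero stays zero. A false difference needs s to differ by arm.

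**The case against.** The best reply is that these are minor secondary outcomes in a 16-subject pilot whose "p-values will be reported without adjustment, consistent with feasibility study design and the" small numbers, and that follow-up is largely common to both arms: daily inpatient review, telephone calls, and clinic at Visits 6 and 10. The artefact rests wholly on assumed rates and amounts to half a patient or less. The case report forms are not included in the document, so items on them cannot be ruled out. All of this stands, and it limits the weight of the point.

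Three stronger readings are tempting, and the documents do not support them.

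- *The neuroma bias must favour PNS.* It would if pain alone drove detection. Device-related contact could raise detection in that arm instead, so the net direction is unknown.
- *Lead-site inspection means the PNS arm's wound is seen more often.* The insertions described are mostly at the groin or buttock (Section 5.5.2, with a popliteal alternative), not at the stump. Unscheduled device visits could add looks, but Section 5.5.9 expects most problems to be handled by telephone.
- *Readmission can show a false difference because other hospitals are missed.* No section shows hospital use differing by arm. Section 8.1 also monitors serious adverse events at each follow-up encounter and classes events that need or prolong a hospital stay as severe. That is a partial second source. It is not linked to the readmission outcome, and the symptoms it lists to ask about do not include hospital stays.

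What remains is the pain route for neuroma and the lack of any fixed measurement for the other two.

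**Conclusion.** The point holds in limited form. For neuroma, the stated source makes detection likely to depend on pain, which the treatment is meant to change, so the recorded comparison cannot separate fewer neuromas from fewer searches. This is an inference about clinical practice, not something the plan states. Its size is unknown: the illustration gives ratios of 0.68 to 0.82, and other assumed detection rates give 0.44 to 1.8.

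For wound healing, the recorded date is imprecise. For readmission, capture may be incomplete, and equal misses would dilute a true difference. Bias between arms is possible for healing through unscheduled visits, but it is not shown for either outcome.

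In this pilot chance will usually outweigh the artefact. The reason to act is that the pilot is meant to refine assessment procedures for a larger trial, where the same artefact could reach significance. This is a cheap improvement, not a flaw that threatens the pilot's feasibility aims.

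**What to change.** 1. **Wound healing.** At Visits 6 and 10, in both arms, add one item to the case report form: amputation wound closed, yes or no. Report the proportion closed at each visit alongside the record-based time to healing in Section 6.3. Confirm that Group 2 attends these visits: Sections 5.5.5 and 5.5.7 say that all subjects do, while Section 5.5.1 describes telephone follow-up for Group 2 after discharge.
2. **Readmission.** At each existing call and visit, ask both arms about any hospital stay since the last contact, at any hospital. Use the answers together with the record for 30-day readmission.
3. **Neuroma.** Report record-based cases as *clinically diagnosed neuroma*, descriptively, with the number of subjects worked up in each arm, and do not call the result incidence. This does not remove the detection problem; it lets a reader see it.

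A scheduled check for focal stump tenderness is not recommended as a substitute for neuroma diagnosis. Tenderness is itself a pain response in unblinded subjects, so it would carry the same dependence on treatment.

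The cost is two short form items at contacts that already take place, and a less favourable label for the neuroma outcome. No visit is added and no treatment changes.
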